9.1. Adverse Events

An AE is any undesirable event that occurs to a participant during a study, whether that event is considered related to Study Drug.

All summaries of AEs will be based on treatment-emergent adverse events (TEAEs) unless specified otherwise.

An adverse event is considered a TEAE if:

- The adverse event first occurred on or after the date of the first dose of study drug; or
- The adverse event was present before the date of the first dose of study drug, but it increased in severity or became serious on or after the date of the first dose of study drug.

9.1.1. Severity of Adverse Events

[figure not shown]
The severity of each AE should be characterized and then classified into one of three clearly defined categories as follows:

- Mild
- Moderate
- Severe

These three categories are based on the Investigator's clinical judgment, which in turn depends on consideration of various factors such as the participant's report and the physician's observations.

The missing severity of an AE will be imputed to "severe".

Version 1.0 | 28-Feb-2025 Page 31 of 56

9.1.2. Relationship to Study Drug

The relationship of each AE to the Study Drug will be based on the Investigator's assessment as to whether there is a reasonable possibility the AE was caused by the Study Drug.

The causal relationship between an AE and the study drug will be categorized as two cases in the CRFs as follows:

Case 1: If AE started while participant was consented under protocol v 2.0, then the categories will be

- Unlikely Related,
- Possibly Related, and
- Probably Related.

The missing relationship to study drug of an AE will be imputed to "Probably Related".

Treatment-related TEAEs are defined as the TEAEs with relationship to study drug is "Possibly Related" or "Probably Related".

Case 2: If AE started while participant was consented under protocol v 3.0 and/or above, then the categories will be

- Not Related, and
- Reasonable Possibility.

The missing relationship to study drug of an AE will be imputed to "Reasonable Possibility".

Treatment-related TEAEs are defined as the TEAEs with relationship to study drug is "Reasonable Possibility."

For the analysis purposes (regardless of protocol amendment version), treatment-related TEAEs are defined as the TEAEs with relationship to study drug is "Possibly Related" or "Probably Related" or "Reasonable Possibility."

[figure not shown]
9.1.3. Serious Adverse Events (SAEs)

A Serious Adverse Event (SAE) includes (but is not limited to) an experience occurring at any dose that results in any of the following outcomes:

- Death,
- Life-threatening,
- In-patient hospitalization,
- A persistent or significant disability/incapacity,
- A congenital anomaly/birth defect, and
- Other medically important event

The number and proportion of participants who experience the event according to MedDRA system organ class (SOC) and preferred term (PT) will be presented by treatment group. TEAEs

Version 1.0 | 28-Feb-2025 Page 32 of 56

will be further summarized, individually, by maximum severity and relationship to study drug. Adverse events related to study drug, AEs leading to withdrawal, SAEs, and deaths will be similarly summarized.

An overall summary of TEAEs will be provided by treatment. This summary will present number and percentage of participants with TEAEs per the following classifications:

- Participants with any TEAEs
- Participants with Treatment-Emergent Drug-Related AEs
- Participants with Treatment-Emergent AEs by Maximum Severity as Mild, Moderate, and Severe.
- Participants with TEAE leading to discontinuation from study
- Participants with Treatment-Emergent SAEs
- Participants with Treatment-Emergent SAEs leading to discontinuation from study
- Participants with Treatment-Emergent SAEs resulting in death

The following summary tables for TEAEs will be presented:

[figure not shown]
- Number and percent of participants reporting treatment-emergent AEs, grouped by MedDRA system organ class and preferred term
- Number and percent of participants reporting treatment-emergent drug-related AEs, grouped by MedDRA system organ class, and preferred term
- Number and percent of participants reporting treatment-emergent AEs, grouped by MedDRA system organ class, preferred term, and maximum severity
- Number and percent of participants reporting treatment-emergent SAEs will be tabulated by system organ class and preferred term and presented by treatment.
- Number and percent of participants reporting treatment-emergent AEs leading to study discontinuation, grouped by MedDRA system organ class and preferred term

For the summary tables above, the SOC terms and PTs will be presented in decreasing order of the total number of participants (frequency) who experienced each AE. System organ class terms and PTs with the same frequency will be presented alphabetically. In the case of multiple occurrences of the same TEAE within the same participant, each participant will only be counted once for each preferred term.

The following data listings for AEs will be provided for each participant by displaying the events captured on the CRF:

- All AEs,
- All serious AEs,
- All AEs leading to study discontinuation, and
- All AEs leading to Death.

Version 1.0 | 28-Feb-2025 Page 33 of 56

In the AE data listings, all AEs will be displayed. AEs that are not treatment-emergent will be flagged in the AE listings.

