# 7.1.10. Unscheduled Visits and Discontinuation due to AEs

For unscheduled visits due to AEs, any assessments conducted will be at the discretion of the Investigator and pertinent to the AE. If a decision is made to discontinue the subject from Study Drug, the Sponsor will be notified immediately. The subject should be followed and treated by the Investigator until the AE has resolved or stabilized (see Section 10.1 – Adverse Events). Restarting the subject on Study Drug will be a mutual decision by the Investigator and the Sponsor. See also Section 9.0 – Early Discontinuation.

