# 7.1.11. Stopping Criteria

Liver chemistry threshold stopping criteria have been designed to ensure subject safety and to evaluate liver event etiology during administration of Study Drug. Potential discontinuation of Study Drug for abnormal liver function tests should be considered by the Investigator in consultation with the designated medical monitor if the study subject meets one or more of the following criteria:

- ALT or AST  $\geq$  4x ULN;
- ALT or AST  $\geq 3x$  ULN and total bilirubin  $\geq 2x$  ULN;
- ALT or AST  $\geq$  3x ULN if associated with the appearance or worsening of fatigue, nausea, vomiting, right upper quadrant pain or tenderness, fever, rash

and/or eosinophilia; or

- ALP elevations, if deemed of liver origin and drug-related as follows:
  - o ALP > 3x ULN;
  - o ALP > 2.5x ULN and total bilirubin > 2x ULN; or
  - o ALP > 2.5x ULN if associated with the appearance or worsening of fatigue, nausea, vomiting, right upper quadrant pain or tenderness, fever, rash and/or eosinophilia.

In the event of discontinuation due to abnormal liver function tests, the subject will be appropriately investigated to determine the potential cause and referred to a physician experienced in the treatment of hepatic disorders.

Study Drug should be discontinued if a subject: (1) positively affirms suicidal ideation in response to questions number 4 or 5 in the Suicidal Ideation section of the C-SSRS, or (2) reports any suicidal behavior or non-suicidal self-injurious behavior since their last visit in response to the C-SSRS Suicidal Behavior questions. The subject should be referred to a psychiatrist or an appropriate health care professional for further evaluation and management.

Bodyweight loss (compared to weight at Baseline Visit [Study Day 1]) of  $\geq$  2 kg resulting in a BMI < 18.5 is an additional stopping criterion.

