#### 9. EARLY DISCONTINUATION

Subjects may choose to discontinue Study Drug or study participation at any time, for any reason, and without prejudice. Moreover, a subject may be withdrawn at any time at the discretion of the Investigator or Sponsor for safety, behavioral or administrative reasons. Discontinued subjects should be followed according to medical practice standards, and the outcome documented. Follow-up is required if the subject is discontinued due to an adverse event (AE). Any comments (spontaneous or elicited) or complaints made by the subject and the reason for termination and the date of stopping the drug must be recorded in the Case Report Form (CRF) and source documents.

The following must be completed and documented in the source documents and CRFs for all subjects who discontinue the study early:

- The reason for early study discontinuation. If the subject is withdrawn for more than one reason, each reason should be documented in the source documents and the most clinically relevant reason should be entered on the CRF.
- Vital signs (blood pressure, temperature and pulse), brief physical and neurologic examination, weight, clinical laboratory tests, 12-lead resting ECG (5 min supine), use of concomitant medications and adverse events should be obtained at discharge prior to release.
- Blood draw for plasma biomarkers
- ADAS-Cog12, MMSE, CDR, ADCS-ADL, NPI, ZBI and C-SSRS (as detailed in Section 7.1.7 Early Termination Visit), if not performed within the last 30 days.

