13.3. Safety Data

Table 7: Safety Data

Table Number	Population	Table Title/Summary
14.3.1 Displays o	f Adverse Events	
14.3.1.1	Safety	Overall Summary of Treatment Emergent Adverse Events
14.3.1.2	Safety	Summary of Treatment Emergent Adverse Events by System Organ Class and Preferred Term
14.3.1.3	Safety	Summary of Treatment Emergent Drug-Related Adverse Events by System Organ Class and Preferred Term
14.3.1.4	Safety	Summary of Treatment Emergent Adverse Events by System Organ Class, Preferred Term, and Maximum Severity
14.3.1.5	Safety	Summary of Serious Treatment Emergent Adverse Events by System Organ Class and Preferred Term
14.3.1.6	Safety	Summary of Treatment Emergent Adverse Events Leading to Study Discontinuation by System Organ Class and Preferred Term
14.3.2 Summary	of Deaths, Other Ser	ious and Significant Adverse Events
14.3.2.1	Safety	Listing of Serious Adverse Events
14.3.2.2	Safety	Listing of Adverse Events Leading to Study Discontinuation
14.3.2.3	Safety	Listing of Adverse Events Leading to Death

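### The SAP's adverse-event discontinuation displays count only exits from the study, so adverse events that stopped Study Drug in participants who stayed in are not identified as such by arm

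*SAP*

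**What the plan says.** **Protocol.** Stopping drug and leaving the study are distinct events.
- Section 9 gives subjects the choice of ending either one.
- Section 7.1.10 makes stopping drug for an adverse event a decision in its own right and adds: "Restarting the subject on Study Drug will be a mutual decision by the Investigator and the Sponsor".
- Section 7.1.11 directs its liver, C-SSRS and body-weight criteria at Study Drug. The liver rule is discretionary: "Potential discontinuation of Study Drug for abnormal liver function tests should be considered by the Investigator".
- On recording, section 9 says "the reason for termination and the date of stopping the drug must be recorded in the Case Report Form".

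**SAP.** The adverse-event discontinuation displays all use study exit.
- The overall TEAE summary in 9.1.3 has two such rows, "Participants with TEAE leading to discontinuation from study" and "Participants with Treatment-Emergent SAEs leading to discontinuation from study".
- Table 14.3.1.6 is titled "Summary of Treatment Emergent Adverse Events Leading to Study Discontinuation by System Organ Class and Preferred Term". Listing 14.3.2.2 and the disposition summary in 7.1 use the same criterion.
- Section 9.1.3 also says "AEs leading to withdrawal, SAEs, and deaths will be similarly summarized", and the safety endpoints in 3.2.1 use similar wording. Neither says whether withdrawal means from drug or from study. The planned tables settle it as study.
- Section 9.2.1 and Table 14.3.5.4 separately summarize, by arm, participants who met at least one post-dose stopping criterion.

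**The concern.** Adverse events that led to stopping drug are a standard way to compare tolerability across 100 mg, 50 mg and placebo. Here the protocol's safety actions are taken on drug, while the tables count exits from the study. Someone whose drug is stopped for an adverse event and later restarted has not left, so no discontinuation row or table identifies that person.

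The reader of the study report would then have a by-arm count of adverse-event drug stops that is too low by an unknown amount. The count would also leave out stop-and-restart cases, which help in judging whether the drug caused the event. The SAP lists its tables explicitly, so a programmer following it would not add the missing display.

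**Working it through.** The plan states no rate of adverse-event drug stops, so there is no figure to reproduce. The check is a reading of every by-arm display that could carry such stops, followed by an illustration on assumed rates.

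**Step 1: discontinuation displays.** Of the seven entries in the overall TEAE summary (SAP 9.1.3), two concern discontinuation, both from the study. Of the six TEAE tables (14.3.1.1 to 14.3.1.6), one does, also from the study. None concerns drug withdrawn or interrupted.

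**Step 2: other displays that might fill the gap.**

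| Display | What it shows | What it lacks |
|---|---|---|
| Table 14.3.5.4 (SAP 9.2.1, 13.3) | By arm, participants meeting at least one liver, C-SSRS or weight criterion | Whether drug was stopped; stops for any other adverse event; a stated split by criterion |
| General TEAE tables (14.3.1.1 to 14.3.1.4) | The events themselves, whether or not the participant left | The action taken with drug |
| Exposure (SAP 6.1.7, 7.4) | Days from first dose to last, inclusive | Any gap in between: a stop with restart does not shorten it |
| Average daily dose (SAP 6.1.7) | May fall after an interruption | A cause; not calculated for placebo |
| Compliance (SAP 7.4) | Tablets taken against planned; 75% to 125% classed as compliant | A cause |

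No planned by-arm display links an adverse event to a drug stop in someone who stays in the study.

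**Step 3: the SAP's own distinction.** The estimands in SAP 3.2 handle dosing deviations by treatment policy and early study discontinuation by a hypothetical strategy. The plan therefore separates the two for efficacy but not in the adverse-event tables.

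**Step 4: size, on assumed rates.** Let s be the share of an arm with an adverse-event drug stop and r the share of those who stay in the study. With 361 per arm (SAP 2.2), true stops = 361 × s and stops displayed = 361 × s × (1 − r). Both s and r are assumptions.

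| s | True stops | r = 10% | r = 30% | r = 50% |
|---|---|---|---|---|
| 2% | 7.2 | 6.5 | 5.1 | 3.6 |
| 5% | 18.1 | 16.2 | 12.6 | 9.0 |

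The number missed runs from 0.7 (7.2 × 0.1) to 9.0 (18.1 × 0.5) per arm.

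**Step 5: effect on the comparison.** Take s = 5% in one arm, 2% in another, and r = 30% in both. The difference in counts falls from 18.1 − 7.2 = 10.8 (unrounded 18.05 − 7.22 = 10.83) to 10.83 × 0.7 = 7.6. The ratio stays at 2.5, because (1 − r) cancels. If r differed by arm, the ratio could move either way.

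**The case against.** The strongest reply is that little is lost.
- Participants who meet a liver, C-SSRS or weight criterion are counted by arm in Table 14.3.5.4 and listed in 16.2.8.5. Liver chemistry has by-visit and shift tables.
- All adverse events are tabulated and listed, and Study Drug administration is listed by participant (16.2.5.1), so individual stop-and-restart cases can be reviewed.
- Safety analysis is descriptive, so no test depends on the missing row.
- The affected group may be small. The protocol sets out no separate visit schedule for people off drug but still in the study, and those who stop for good and attend an early termination visit are counted already.

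Most of this stands, and it rules out several stronger readings that a reader might infer.
- *Drug stops, including liver stops, appear in no by-arm table.* Not supported: Table 14.3.5.4 and the general TEAE tables carry the criteria and the events. What is missing is their identification as drug stops.
- *The count is biased toward no difference.* Not shown: Step 5 shows that a common retained share leaves the ratio unchanged, and the documents give no shares.
- *A known clinical liver signal is being hidden.* Not supported: the liver findings in Protocol 2.2 are in rats, and Protocol 2.3 reports no discontinuation due to adverse events in either Phase 2 study.
- *The data needed are certainly in hand.* Not shown: Protocol 9 requires the drug stop date and a reason for termination, and Protocol 10.1 to 10.3 name severity and relationship for EDC. No section shows a field for the reason for a temporary stop.

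The reply does not remove the gap. Meeting a discretionary threshold is not the same as having drug stopped, other adverse events are outside Table 14.3.5.4, and listings do not give a count by arm.

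**Conclusion.** The point holds as a reporting gap that should be closed. Followed as written, the SAP identifies adverse-event discontinuations only when the participant leaves the study, while the protocol provides for drug to be stopped, and possibly restarted, without study exit. Table 14.3.5.4 is a partial substitute.

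The size cannot be determined from the documents. The range of about 1 to 9 missed per arm rests entirely on the assumed stop rates and retained shares. Neither the co-primary analyses nor any planned significance test is affected.

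**What to change.** In the SAP, before unblinding:
- State in 3.2.1 and 9.1.3 whether adverse events leading to withdrawal means from Study Drug, from the study, or both.
- Add by-arm rows to the overall TEAE summary, an SOC/PT table and a listing for TEAEs leading to Study Drug discontinuation. Add the same for interruption with restart where the CRF and drug-administration records support it. If they do not, say so in the SAP.
- In Table 14.3.5.4, report each criterion separately and, where recorded, whether drug was stopped and whether it was restarted.
- Keep the existing study-discontinuation rows, table and listing.

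This changes reporting only and leaves every clinical stopping and restarting rule as it is. The cost is a small amount of SAP text and programming, plus a check of what the CRF captured, since the study has already been terminated (SAP 2.1). The reported figure for adverse-event drug stops may come out slightly less favourable.

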9.2. Clinical Laboratory Evaluations

The following clinical laboratory tests will be performed during the Screening Period, Baseline (Study Day 1) pre-dose, and at all follow-up visits (Week 4, Week 16, Week 28, Week 40, Week 52, Week 64, and Week 76/ET/ED).

Table 3: Protocol-Required Safety Laboratory Tests

Hematology							
Erythrocytes (RBC)	Eosinophils (EOS)	Leukocytes (WBC)					
Hemoglobin (HGB)	Lymphocytes (LYM)	Eosinophils/Leukocytes (EOSLE)					
Hematocrit (HCT)	Monocytes (MONO)	Lymphocytes/Leukocytes (LYMLE					
Platelets (PLAT)	Neutrophils (NEUT)	Monocytes/Leukocytes (MONOLE)					
Basophils (BASO)	Basophils/Leukocytes (BASOLE)	Neutrophils/Leukocytes (NEUTLE)					
Serum Chemistry							
Alanine aminotransferase (ALT)	Calcium (CA)	Phosphate (PHOS)					
Albumin (ALB)	Chloride (CL) Gamma-glutamyl transferase (GGT) Globulin (GLOBUL) Glucose (GLUC)	Potassium (K)					
Alkaline phosphatase (ALP)		Protein (PROT)					
Aspartate aminotransferase (AST)		Sodium (SODIUM)					
Bicarbonate (BICARB)	Creatinine (CREAT)	Urea Nitrogen (UREAN)					
Bilirubin (BILI)	Lactate dehydrogenase (LDH)	Urate (URATE)					
Urinalysis*							
Color (COLOR)	Leukocyte esterase (LEUKASE)	Protein (PROT)					
Glucose (GLUC)	Nitrite (NITRITE)	Specific gravity (SPGRAV)					
Ketones (KETONES)	рН (РН)	Occult Blood (OCCBLD)					

[figure not shown]
^{*} A "reflex" microscopic examination will be performed if protein, occult blood, nitrites, or leukocyte esterase is present on the basic analysis.

Screening Period: During the Screening Period only, bloods will be drawn for TSH, free T4, Vitamin B12, HepBsAg, HCV-Ab, HbA1C (diabetic participants only) and plasma P-tau181 (Note – plasma collection for P-tau181 not required if participant has documented evidence of AD pathophysiology prior to screening). Urine to screen for drugs of abuse (amphetamines, cocaine, opiates and phencyclindine) will also be collected during the Screening Period.

All hematology, chemistry, and urinalysis laboratory results will be presented in SI units, if available. Only laboratory parameters in the Table 3, will be tabulated.

The observed values and changes from baseline of all quantitative safety laboratory results for clinical chemistry, hematology, and urinalysis (only for pH and Specific Gravity results) will be summarized using descriptive statistics showing the number of observations (n), mean (SD), median, minimum, and maximum value. A separate summary table with the number and percentage of participants for each categorical urinalysis parameter (glucose, protein, occult blood, ketone, nitrite, and leukocyte esterase) will be provided.

Version 1.0 | 28-Feb-2025 Page 34 of 56

Baseline values for all clinical chemistry, hematology, and urinalysis parameters will be categorized as being below the normal range (Low), within the normal range (Normal), and above the normal range (High). Shift from baseline tables will present the number and percentage of participants who have observations that are Normal, Low, or High when such range characterizations are available. Shift tables will be presented for values shifting from Baseline (Study Day 1) to the Week 76/ET/ED.

Listings of all observed chemistry, hematology, and urinalysis laboratory data will be provided. Laboratory results outside the normal range will be flagged. The abnormal values will be flagged with 'L' (low) for values below the lower limit of the laboratory's normal range or 'H' (high) for values above the upper limit of the laboratory's normal range. Abnormal values will be graded as not clinically significant (NCS) or clinically significant (CS).

Abnormal results from the microscopic examination will be listed. All other laboratory assessments will only be listed.

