Simufilam was tested in single dose and repeat dose oral toxicity studies of up to 6 months in rats and 9 months in dogs. A 6-month repeat dose oral toxicity study in rats (PTI-125-NC-049) used the same doses as a 28-day study (50, 500 and 1000 mg/kg/day), which found 500 mg/kg/day to be the no-adverse-effect-level (NOAEL). In the 6-month study, the toxicological response was characterized by decreased body weights and adverse structural and functional alterations in the liver of 500 and 1000 mg/kg/day animals, including increased hepatic weight, hepatocellular hypertrophy and vacuolation, single/multiple basophilic/ eosinophilic/clear cell focus, hepatocellular degeneration, pigmentation, and oval cell hyperplasia. The presence of bile pigment was consistent with cholestasis. These findings correlated with changes to the clinical chemistry profile, including increased ALP and total/direct bilirubin. Over the 1-month recovery period, there was complete recovery of the hepatocellular degeneration and partial recovery of hepatocellular hypertrophy; other microscopic findings in the liver remained. The NOAEL in this 6-month study was 50 mg/kg/day (equivalent to 300 mg/m^2), corresponding to a safety margin of 6- and 1.6-fold based on Cmax and AUC over the 100 mg b.i.d. dose in human subjects. A second 6-month repeat dose oral toxicity study in rats determined the 6-month NOAEL in the rat to be < 125 mg/kg/day, based on hepatocellular vacuolation in both sexes and hepatocellular hypertrophy in females at 125 and 250 mg/kg.

In a 9-month toxicity study in dogs (PTI-125-NC-050), the no-effect-level (NOEL) of simufilam was 25 mg/kg. The high dose of 200 mg/kg/day was decreased to 150 mg/kg/day after 1 month due to bodyweight loss considered unsustainable for 9 months. Clinical signs were slight hypoactivity and incidences of slight muscle fasciculations early in the study, and salivation. There were no pathology findings, but the high dose was considered adverse due to two unexplained deaths. The 75 mg/kg/day NOAEL (equivalent to 1500 mg/m²) provides 38- and 19-fold safety margins based on Cmax and AUC over the 100 mg b.i.d. dose in subjects.

Simufilam showed no mutagenic or clastogenic responses in a standard battery of genotoxicity assays.

[figure not shown]

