3.2.1. Safety Endpoints

The safety endpoints of this study include the following:

• Incidence of adverse events (AEs) including treatment-emergent, serious, related to study

Version 1.0 | 28-Feb-2025 Page 16 of 56

drug, and leading to withdrawal along with AEs by severity and relationship to study drug

- Mean change in clinical laboratory values from baseline to Weeks 4, 16, 28, 40, 52, 64 and 76. Shifts in the normality of clinical laboratory values from baseline to Weeks 4, 16, 28, 40, 52, 64 and 76.
- Mean change in vital signs (blood pressure [supine], temperature, pulse rate) from baseline to Weeks 4, 16, 28, 40, 52, 64 and 76.
- Mean change in body weight from baseline to Weeks 4, 16, 28, 40, 52, 64 and 76.
- Shifts in physical exam (PE) findings from baseline to Weeks 4, 16, 28, 40, 52, 64 and 76.
- Shifts in neurological exam (NE) findings from baseline to Weeks 4, 16, 28, 40, 52, 64 and 76.
- Mean change in ECG parameters from baseline to Weeks 4, 40 and 76.
- Concomitant medications/treatments usage
- Shifts in the C-SSRS from baseline to Weeks 4, 16, 28, 40, 52, 64 and 76.

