8.8. Pooling With Other Studies

Data from Protocol PTI-125-06 will be pooled with data from Protocol PTI-125-07. These pooled analyses will include data from weeks 0-52 from Protocol PTI-125-06 to match the duration of Protocol PTI-125-07. Objectives and estimands for the pooled data will mirror those in Protocol

Version 1.0 | 28-Feb-2025 Page 30 of 56

PTI-125-07. Analyses will also be similar but will include an additional categorical fixed effect of study. These pooled data will be analyzed using the co-primary and multiplicity adjusted secondary endpoints and by the subgroups defined by baseline composite severity / baseline P-tau categories.

Additional analyses may be applied to the pooled data based on the findings of the PTI-125-06 study.

9. Safety and Tolerability Analysis

All safety analyses will be performed on the safety analysis set.

Safety measures including AEs, clinical laboratory values, physical examination findings, neurologic examination findings, vital signs, ECGs, and concomitant medication usage will be summarized descriptively. No inferential statistical tests will be performed, unless otherwise specified. For quantitative variables, descriptive statistics including number of observations, mean, median, standard deviation, minimum, and maximum will be presented for observed and change from baseline values at each study visit. Qualitative variables will be summarized using counts and percentages.

For all safety and tolerability analyses, participants will be analyzed by the actual treatment and dose received and, if applicable, overall.

All safety and tolerability data will be presented in participant listings.

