9.2.1. Stopping Criteria

Potential discontinuation of study drug for abnormal liver function tests should be considered if the study participant meets one or more of the following liver chemistry threshold stopping criteria:

- ALT or AST \geq 4x ULN;
- ALT or AST $\geq 3x$ ULN and total bilirubin $\geq 2x$ ULN;
- ALT or AST \geq 3x ULN if associated with the appearance or worsening of fatigue, nausea, vomiting, right upper quadrant pain or tenderness, fever, rash and/or eosinophilia;

or

- ALP elevations, if deemed of liver origin and drug-related as follows:
 - \circ ALP > 3x ULN;
 - \circ ALP > 2.5x ULN and total bilirubin > 2x ULN; or
 - ALP > 2.5x ULN if associated with the appearance or worsening of fatigue, nausea, vomiting, right upper quadrant pain or tenderness, fever, rash and/or eosinophilia,

where ULN = Upper Limit of Normal.

Study drug should be discontinued if a participant: (1) positively affirms suicidal ideation in response to questions number 4 or 5 in the suicidal ideation section of the C-SSRS, or (2) reports any suicidal behavior or non-suicidal self-injurious behavior since their last visit in response to the C-SSRS Suicidal Behavior questions.

Bodyweight loss (compared to weight at Baseline Visit [Study Day 1]) of \geq 2 kg resulting in a BMI < 18.5 is an additional stopping criterion.

Individual results of stopping criteria will be listed and summarized by presenting the number and percentage of participants who meet at least one post-dose stopping criteria.

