14.3.5 Laboratory Data Summary Tables		

Version 1.0 | 28-Feb-2025 Page 46 of 56

[figure not shown]
[figure not shown]

Table Number	Population	Table Title/Summary
14.3.5.1.1	Safety	Summary of Laboratory Results - Serum Chemistry
14.3.5.1.2	Safety	Summary of Shift from Baseline in Serum Chemistry Results
14.3.5.2.1	Safety	Summary of Laboratory Results-Hematology
14.3.5.2.2	Safety	Summary of Shift from Baseline in Hematology Results
14.3.5.3.1	Safety	Summary of Laboratory Results -Urinalysis
14.3.5.3.2	Safety	Summary of Categorical Urinalysis Results
14.3.5.4	Safety	Summary of Stopping Criteria by Treatment
14.3.6 Other Safe	ety Data Summary Ta	ables
14.3.6.1	Safety	Summary of Vital Signs Results
14.3.6.2	Safety	Summary of Weights and BMI
14.3.7.1	Safety	Summary of Concomitant Medications
14.3.7.2	Safety	Summary of Concomitant Medications-Cognitive Enhancers Taken Prior to First Dose of Study Drug
14.3.7.3	Safety	Summary of Concomitant Medications-Cognitive Enhancers Taken Post First Dose of Study Drug
14.3.8.1	Safety	Summary of Electrocardiogram Quantitative Results
14.3.8.2	Safety	Summary of Electrocardiogram Interpretation Results
14.3.8.3	Safety	Summary of Observed Categorical ECGs
14.3.8.4	Safety	Summary of Change from Baseline Categorical ECGs
14.3.9.1	Safety	Summary of Physical Examination (Brief) Results
14.3.9.2	Safety	Summary of Neurological Examination (Brief) Results
14.3.10.1	Safety	Summary of Columbia-Suicide Severity Rating Scale (C-SSRS) Suicidal Ideation and Suicidal Behavior Experienced at Any Time Post-Treatment
14.3.10.2	Safety	Summary of Columbia-Suicide Severity Rating Scale (C-SSRS) Suicidal Ideation and Suicidal Behavior by Study Visit
14.3.10.3	Safety	Shift of Columbia-Suicide Severity Rating Scale (C-SSRS) Suicidal Ideation and Suicidal Behavior from Pre-Treatment to Post-Treatment
14.3.10.4	Safety	Shift of Columbia-Suicide Severity Rating Scale (C-SSRS) Suicidal Ideation Scores from Baseline to Treatment Period
14.3.11.1	MRI Sub-study	Summary of MRI Findings

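### SAP 9.2 plans laboratory shift tables to Week 76/ET/ED only, while SAP 3.2.1 names shifts at seven visits, so six of the seven time points are not tabulated

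*SAP*

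**What the plan says.** SAP 3.2.1 lists as a safety endpoint "Shifts in the normality of clinical laboratory values from baseline to Weeks 4, 16, 28, 40, 52, 64 and 76". That is seven post-baseline time points.

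SAP 9.2 has laboratory tests performed at screening, at baseline and "at all follow-up visits (Week 4, Week 16, Week 28, Week 40, Week 52, Week 64, and Week 76/ET/ED"), so the data for all seven exist. For the analysis, however, 9.2 states: "Shift tables will be presented for values shifting from Baseline (Study Day 1) to the Week 76/ET/ED". In SAP Table 7 the shift outputs are 14.3.5.1.2 (chemistry) and 14.3.5.2.2 (hematology). The chemistry title, "Summary of Shift from Baseline in Serum Chemistry Results", mentions neither visit nor worst value. SAP section 10 records changes from the planned analysis as not applicable, so it does not reconcile the two statements.

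Other planned outputs touch the same data:

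- The opening of SAP section 9 says that descriptive statistics, including minimum and maximum, "will be presented for observed and change from baseline values at each study visit".
- For listings, 9.2 says: "Laboratory results outside the normal range will be flagged".
- SAP 9.2.1 reports the "number and percentage of participants who meet at least one post-dose stopping criteria".

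**The concern.** A declared safety endpoint is only partly delivered by the analysis section. A last-visit shift table answers whether participants ended the study out of range. It does not answer how many went out of range on treatment.

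The difference matters most for liver chemistry. Protocol 2.2 describes "adverse structural and functional alterations in the liver of 500 and 1000 mg/kg/day animals" in a 6-month rat study, with raised ALP and bilirubin, and gives a 1.6-fold AUC margin at that study's NOAEL over 100 mg b.i.d. Protocol 7.1.11 sets liver thresholds. A safety reader will want the number of participants per arm with mild or moderate elevations at any visit, not only those still elevated at the end.

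**Working it through.** The plan gives no figure on this point to reproduce. The check is a comparison of passages, a count, and an illustration on stated assumptions.

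**1. Count of time points.** Named in 3.2.1: Weeks 4, 16, 28, 40, 52, 64 and 76, which is 7. Tabulated under 9.2: Week 76/ET/ED, which is 1. Not tabulated: 7 − 1 = 6.

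**2. One participant traced through.** ALT Normal at baseline, High at Week 16, Normal at Week 76. The 9.2 table compares baseline with the last visit only, so the participant is counted as Normal-to-Normal.

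**3. Where else that participant is counted by arm.**

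- By-visit statistics: the value may be the Week 16 maximum for the arm, but there is no count of participants outside the range.
- Listings: flagged, not counted.
- Stopping-criteria table (9.2.1): counted at any post-dose time, but for ALT/AST only at 4x ULN or more, or at 3x or more with raised bilirubin or with symptoms or eosinophilia. Values from 1x to 3x ULN never qualify. Values from 3x to below 4x without those features do not qualify either.
- Adverse-event tables (9.1.3): counted if the investigator reports the abnormality as an event. Protocol 10.1 gives new clinically significant laboratory abnormalities as an example.

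What is left uncounted in any planned laboratory table is the out-of-range value at an intermediate visit that meets no stopping criterion.

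**4. Illustration of size.** Assume a two-state chain (Normal/High) over 7 visits, Normal at baseline, with per-visit prevalence p and probability r that a High value is still High at the next visit.

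- q = P(High next | Normal now) = p(1 − r)/(1 − p)
- P(ever High) = 1 − (1 − q)^7
- P(High at last visit) = h₇, from h₀ = 0 and hₖ₊₁ = r·hₖ + q·(1 − hₖ)
- Share of ever-High participants shown as Normal-to-Normal = 1 − h₇ / P(ever High)

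With p = 0.02 and independent visits (r = p), q = 0.02. P(ever High) = 1 − 0.98^7 = 0.1319, h₇ = 0.02, and the hidden share is 1 − 0.02/0.1319 = 0.848. At the planned 361 per arm with every visit attended, 361 × 0.1319 = 47.6 participants are ever High and 361 × 0.02 = 7.2 are High at the last visit.

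| Persistence r | p = 1% | p = 2% | p = 5% |
|---|---|---|---|
| independent visits (r = p) | 85.3% | 84.8% | 83.4% |
| 0.3 | 79.4% | 79.1% | 78.4% |
| 0.6 | 65.2% | 65.0% | 64.7% |
| 0.9 | 25.5% | 25.5% | 25.4% |

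Persistence drives the answer and prevalence hardly matters. The documents supply neither.

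**5. The last-visit column.** SAP 6.1.5 maps early-termination visits to scheduled windows by study day; Week 76 is Days 492–575. An early-termination draw on, say, Day 300 maps to Week 40 (Days 240–323). Section 9.2 nevertheless labels its column Week 76/ET/ED and does not say whether that draw enters it. If it does not, the participant drops out of the only shift table. SAP 2.1 says that the study was stopped early, so this may affect many participants; the documents do not say how many.

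**The case against.** The strongest reply is that the gap is narrow. A clinically significant transient abnormality reported as an adverse event is counted once per participant by preferred term and maximum severity. Stopping-criterion values are counted at any time. By-visit maxima show the extremes, everything out of range is flagged in listings, and an independent board reviews safety periodically. Safety analysis is descriptive. Protocol 11.4 asks only for descriptive summaries of change and requires no shift tables, and neither document promises a worst-value laboratory table. The shell titles do not themselves restrict the tables to Week 76.

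Most of this stands, and it limits the point. It does not remove it. The adverse-event route depends on investigator judgement, the maximum is not a count, and the explicit sentence in 9.2 governs shells that are silent. The SAP itself made by-visit shifts an endpoint.

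Three stronger inferences are tempting and should be resisted:

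- A reader might infer that transient laboratory abnormalities vanish from the safety reporting. They do not; only the shift tables miss them.
- A reader might divide an assumed duration by the treatment period, for example 12/76 = 16% and 24/76 = 32%, and call that the visible share. Nothing in the documents supports such a duration, random onset, or 76 weeks of follow-up for all. At an assumed 40 weeks the same division gives 12/40 = 30% and 24/40 = 60%. An elevation that prompts discontinuation may also still be present at the termination draw.
- A reader might take the rat data as evidence for elevations that resolve on drug. The findings arose under continuous dosing, and recovery was assessed over a 1-month recovery period. They justify interest in liver values by arm; a persistent effect would appear in a last-visit table.

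**Conclusion.** The inconsistency is real and rests on the text alone: 6 of the 7 time points in the declared endpoint have no shift table, and an excursion that resolves before the last visit is tabulated as no shift. The practical loss is confined to participant counts by arm for sub-threshold out-of-range values at intermediate visits.

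Its size cannot be established from the documents. The range of about 25% to 85% of ever-High participants is an illustration that assumes 1%–5% prevalence per visit, persistence from none to 0.9, and seven attended visits; early termination would alter it. This should be corrected before the tables are produced. It does not threaten the safety database or any efficacy conclusion.

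**What to change.** - Change SAP 9.2 so that shifts are tabulated from baseline to each scheduled visit, matching 3.2.1, and retitle shells 14.3.5.1.2 and 14.3.5.2.2 accordingly.
- Add a shift from baseline to worst post-baseline value, low and high separately, for each parameter and arm. Include unscheduled results, and state that this overrides the 6.1.5 preference for scheduled over unscheduled values in the same window.
- State whether the last column is the Week 76 window only or the last available on-study value, and how early-termination values mapped under 6.1.5 enter it.

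Narrowing 3.2.1 to the last visit would also remove the contradiction, but would leave the counts unreported. The cost of the recommended change is programming and reading a few more descriptive tables from data already collected at every visit. No estimand, alpha allocation or efficacy result changes.
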